2.7.4.2 Vital signs

Systolic/diastolic blood pressure, radial pulse rate (over a 30s interval), respiratory rate and body temperature will be recorded at Visit 1 (screening), Visit 101 (start of treatment), Visit 106 or TD (Day 113) and Follow-up Visit 202/PSD (Day 169).

Vital signs data, including changes from baseline, will be summarized for each visit using descriptive statistics (n, mean, SD, minimum, median, and maximum).

2.7.4.3 Post-inhalation events

Events occurring within 5 minutes after inhalation of the study treatment (post-inhalation events) will be observed at the site by site personnel at Visit 101 (start of treatment), Visit 102 (Day 8), Visit 103 (Day 29), Visit 104 (Day 57), Visit 105 (Day 85) and Visit 106 or TD (Day 113). If the event is determined to be an adverse event, this should be recorded on the Adverse Event eCRF. In addition, event details will also be captured in the Post-inhalation Adverse Event eCRF. For post-inhalation events that are determined not to be an adverse event, event details will be recorded in the Post-inhalation clinical events eCRF.

A separate PK sub-study is included in this study which collects additional PK samples. Patients included in this sub-study will provide 1 serum specimen per specified interval at Visit 101 (start of treatment) and Visit 103 (Day 29): pre-dose, 0-1, 1-2, 3-4 and 5-6 h. Descriptive statistics (n, mean, SD, minimum, median and maximum) will be provided for the PSSAS by scheduled visit and time point.

All PK data will be presented in individual patient data listings.

2.9 PD and PK/PD analyses

The independent bio-analytical report (including PK model and if possible PK/PD model) will be done by Ventiv or Novartis and is not covered in this SAP.

2.10 Patient reported outcomes

Quality of Life Questionnaire-Bronchiectasis (QoL- B)

QoL-B is assessed at Visit 2 (Baseline), Visit 102 (Day 8), Visit 103 (Day 29), Visit 104 (Day 57), Visit 105 (Day 85), Visit 106 or TD (Day 113), Follow-up Visit 201 (Day 141) and Follow-up Visit 202 or PSD (Day 169).

The QoL-B consists of 37 items across 8 domains: Physical, Role Functioning, Vitality, Emotional Function, Social Functioning, Treatment Burden, Health Perception and Respiratory Symptoms. Each of the 37 items is scored from 1 to 4.

Items in the questionnaire are expressed either 'negatively' or 'positively', therefore a number of items must be recorded before the scores for each of the domains are calculated. The score is calculated by adding the score obtained for each item of a domain (scale), after any necessary recoding. Scoring for each domain can be computed only if at least half the items have been completed. If not, then the domain should not be scored and should be considered missing for that particular person who filled out the questionnaire.

[figure not shown]
[figure not shown]
Descriptive statistics will be provided for each domain score for all applicable visits for the FAS by treatment arm [and](#) pooled arms by continuous and cyclic regimens. Changes from baseline to each post-baseline visit will also be summarized. For the QoL-B Respiratory Symptom Score (RSS), further summaries will be provided for:

- Patients with/without pulmonary exacerbations during the treatment period
- Patients with overall study drug compliance $\geq 80\%$

The change from baseline in QoL-B RSS will be analyzed using a linear repeated measure model. The model will contain treatment, baseline macrolide use, visit (visits 102 to 202), and treatment-by-visit interaction as fixed effects with baseline QoL-B RSS, baseline-by-visit interaction as covariates. The within-patient correlation will be modeled using the unstructured covariance matrix in the mixed model. If the model does not converge, then the compound symmetry covariance structure will be used. The restricted maximum likelihood method will be used.

QoL-B correlation with other patient reported outcome measures will be performed by RTI health solutions; consequently these are not detailed within this SAP.

Details on deriving the domain scores can be found in [Section 5.5](#).

2.12 Interim analysis

No interim analysis of efficacy is planned for this study.

The final analysis will be performed after the database is locked, the treatment assignments are unblinded using the actual randomization, and the database released.

An independent DMC is set-up to review safety data and provide the Sponsor with guidance on safety issues. SAE listings generated from the Novartis safety database, ARGUS, will be reviewed monthly by the DMC. The DMC will also perform a pre-planned review of AE and additional pre-defined safety data when approximately 50% of patients have completed the 28 days of treatment.

The membership of the DMC and the responsibilities of the DMC, [REDACTED] will be defined in a separate ‘DMC Charter’ document. The DMC Charter will include information about data flow, purpose and timings of DMC meetings, communication strategy, procedures for ensuring confidentiality, procedures to address conflicts of interest and statistical monitoring guidelines.

3 Sample size calculation

[figure not shown]
Sample size estimation was based on a difference of 2.0 log₁₀ CFU/g, with standard deviations of 2.0 log₁₀ CFU/g. The assumptions were based on conservative estimates from published results ([Konstan et al 2011a](#), [Konstan et al 2011b](#), [Barker et al 2000](#), and [Wilson et al 2013](#)).

As there are 3 primary comparisons between the 3 doses versus placebo, the Bonferroni multiplicity adjustment has been used (0.05/3) for sample size calculation. Using $\alpha=1.67\%$ (2-sided) and 90% power, the sample size estimation yielded $n = 36$ patients per treatment arm as valid for intent-to-treat (ITT) analyses. This takes into account an approximate 20%-discontinuation rate. For the primary efficacy analysis, patients from TIP continuous and TIP cyclical regimen within the same cohort will be pooled as they receive exactly the same treatment during the first 28 days. Placebo patients will be pooled across the 3 cohorts, as the number of placebo capsules is not expected to influence the change in *P. aeruginosa* bacterial counts. With the current study design, the power is 94% to detect a reduction of 2.0 log₁₀ CFU/g for each dose level versus placebo.

For calculation of sample size, NQuery Advisor version 7.0 module MTTO-1 was used.

4 Change to protocol specified analyses

The annual rate of pulmonary exacerbations will be summarized overall. Analyses on the number of pulmonary exacerbations will only be performed overall and not by exacerbation category.

5 Appendix

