DMC	Data Monitoring Committee
DSPC	1, 2-distearoyl-sn-glycero-3-phosphocholine
eGFR	estimated Glomerular Filtration Rate
ENR	Enrolled Set
FAS	Full Analysis Set
FEF ₂₅₋₇₅	Forced Expiratory Flow at 25-75%
FEV ₁	Forced Expiratory Volume at 1 Second
FVC	Forced Vital Capacity
eCRF	electronic Case Report Form
ISC	Independent Study Coordinators
IRT	Interactive Response Technology
MedDRA	Medical Dictionary for Drug Regulatory Affairs
MIC	Minimum Inhibitory Concentration
o.d.	once a day
PCR	Protein-creatinine ratio
	
	
PK	Pharmacokinetics
PKAS	Pharmacokinetic Analysis Set
PKSSAS	Pharmacokinetic Sub-Study Analysis Set
PPS	Per-Protocol Set
PRO	Patient Reported Outcomes
PSD	Premature Subject/Patient Discontinuation
PT	Preferred Term
QoL	Quality of Life
QOL-B	Quality of Life Questionnaire for Bronchiectasis
RAN	Randomized population
SAF	Safety Set
SAP	Statistical Analysis Plan
SOC	System Organ Class

█
TBL

█
Total Bilirubin

TD

Study Treatment Discontinuation

TIP

Tobramycin inhalation powder

TFLs

Tables, Figures, Listings

ULN

Upper Limit of Normal

WHO

World Health Organization

1 Introduction

This statistical analysis plan (SAP) is based on the amended protocol version 02 dated 09th February 2018, and the business decision to close the trial earlier than planned (but not due to safety or efficacy reasons) by the Novartis. Recruitment has been stopped on 02nd October 2018 with 107 patients randomized as against 180 patients initially planned. With this premature closure and reduced sample size, the inferential analysis, regardless if it's pre-defined, can be considered as exploratory, the results obtained should be interpreted with the caution. The plan provides a technical and detailed elaboration of the statistical analyses of the efficacy, safety and tolerability of different doses of tobramycin inhalation powder (TIP) in patients with Non-Cystic Fibrosis Bronchiectasis and pulmonary *P. aeruginosa* infection. The specifications for tables, figures, and listings (TFLs) will be included in a separate document.

A clinical study report (CSR) will be written based on the results of the statistical analyses planned within this SAP. Results will also be used for the various publications.

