1.1 Study design

This is a blinded, randomized, dose and regimen finding trial utilizing a 3 treatment cohort design where active TIP, TIP/Placebo cyclical, or placebo in addition to the local standard care within each cohort are delivered once or twice daily (Figure 1). The study will implement a within-cohort blinding approach. This allows assessment of the tolerability (defined as the rate of local AEs) of different doses and regimens of TIP, and also saves the treatment burden that would be imposed for blinding across all arms. Note that all of the patients in the study would need to inhale the maximal dose of 10 capsules every day (5 morning + 5 evening) to maintain the blind between cohorts (different dose levels) and within a cohort (different regimens).

Approximately 180 eligible patients will be randomized to 1 out of the 3 cohorts in a ratio of 1:1:1. The patients within each cohort will be randomized to blinded TIP or placebo with the following randomization scheme: TIP: TIP/placebo cyclical: placebo, in a 2:2:1 ratio.

At Visit 101 (see protocol [Table 6-1 – Assessment schedule]), all eligible patients will be randomized via Interactive Response Technology (IRT) to 1 of the treatment arms with the randomization strata (use of macrolides as part of their standard of care therapy yes/no). To evaluate serum pharmacokinetics (PK) in approximately 16 patients on active treatment, at least 20-22 patients from each cohort (at least 60 total patients) will participate in a PK sub-study. To ensure a balanced distribution across cohorts, this will be captured in IRT. The investigator or his/her delegate will contact the IRT after confirming that the patient fulfills all the inclusion/exclusion criteria. The IRT will assign a randomization number to the patient, which will be used to link the patient to a treatment arm and will specify a unique medication number for the first package of investigational treatment to be dispensed to the patient. The randomization number will not be communicated to the user.

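### SAP Section 3 gives 94% power for the current design, but that figure belongs to 180 patients; at the 107 randomized the same calculation gives about 73%.

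*SAP*

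**What the plan says.** SAP Section 3 sets out the sizing. "Sample size estimation was based on a difference of 2.0" log10 CFU/g "with standard deviations of 2.0" log10 CFU/g, and "the Bonferroni multiplicity adjustment has been used (0.05/3) for sample size calculation". At 90% power this yielded 36 patients per group, and "This takes into account an approximate 20%-discontinuation rate". After explaining that the continuous and cyclical arms are pooled within each dose and that placebo is pooled across cohorts, it concludes: "With the current study design, the power is 94% to detect a reduction of 2.0" log10 CFU/g for each dose level. The text repeats Protocol Section 9.7, which was written for 180 patients.

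SAP Section 1 says: "Recruitment has been stopped on 02nd October 2018 with 107 patients randomized as against 180 patients initially planned". It adds that the inferential analysis can therefore be considered exploratory and that the results call for caution. SAP Section 1.1 still describes about 180 patients, "randomized to 1 out of the 3 cohorts in a ratio of 1:1:1", then 2:2:1 within each cohort. Neither Section 3 nor the visible part of Section 4 gives power or precision for 107 patients.

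**The concern.** Section 1 and the 94% sentence in Section 3 cannot both describe the same trial. The SAP was written after recruitment had closed. The base calculation in Section 3 is reported in the past tense, whereas the 94% is in the present tense and tied to the current design.

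The trial is meant to guide dose selection (Protocol Section 1.2). The SAP keeps formal hypotheses, p-values and family-wise error control at 5% for the primary comparison (SAP Sections 2.1.2 and 2.5.2), so doses will be reported as significant or not. A reader who takes Section 3 at face value would judge a non-significant dose against a miss probability of about 6% for a true 2.0 log10 effect. If the real probability is several times larger, an effective dose could be set aside too readily.

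**Working it through.** **Inputs**
- Difference 2.0, SD 2.0 (log10 CFU/g), two-sided alpha 0.05/3 = 1.67% per comparison, 20% loss: SAP Section 3.
- Planned groups: 36 pooled placebo and 24 per active arm, so 2 × 24 = 48 per dose: Protocol Section 3.2.
- Ratios 1:1:1 and 2:2:1: SAP Section 1.1.
- 107 randomized: SAP Section 1.

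**Formula.** Two-sample t-test: df = n₁ + n₂ − 2, noncentrality = difference / (SD × √(1/n₁ + 1/n₂)), critical value t at 1 − alpha/2, power from the noncentral t distribution.

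**Reproducing the plan's figures**

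| Case | n per dose | n placebo | Noncentrality | Critical t | Power |
|---|---|---|---|---|---|
| 36 per group, less 20% | 28.8 | 28.8 | 3.79 | 2.47 | 90.4% |
| 48 vs 36, less 20% | 38.4 | 28.8 | 4.06 | 2.46 | 94.2% |
| 48 vs 36, no loss | 48 | 36 | 4.54 | 2.44 | 98.0% |

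The stated 90% and 94% both reproduce. The 94% therefore belongs to 180 randomized and already includes the 20% loss.

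**Same method at 107**
- Placebo: 107 / 5 = 21.4. Per dose: (107 / 3) × 4/5 = 28.5.
- After 20% loss: 21.4 × 0.8 = 17.1 and 28.5 × 0.8 = 22.8.

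| Loss | n per dose | n placebo | Noncentrality | Critical t | Power |
|---|---|---|---|---|---|
| 20% | 22.8 | 17.1 | 3.13 | 2.50 | 73.1% |
| 10% | 25.7 | 19.3 | 3.32 | 2.49 | 79% |
| 5% | 27.1 | 20.3 | 3.41 | 2.49 | 82% |
| None | 28.5 | 21.4 | 3.50 | 2.48 | 84.1% |

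Whole-number groups of 23 vs 17 give 73.0%, and 22 vs 17 give 72.0%. The normal approximation gives 76.9% with 20% loss and 86.5% with none; at 180 patients with 20% loss it gives 95.2%.

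**Planned test.** Step-wise Dunnett, simulated with variance pooled over all four groups and 20% loss, gives 77% if only one dose works and 83% per dose if all three work.

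**Detectable difference.** Solving the t-test calculation for 94% power at 22.8 vs 17.1 gives 2.63 log10.

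**Precision.** The standard error of a dose-placebo difference is 2.0 × √(1/38.4 + 1/28.8) = 0.49 as planned and 2.0 × √(1/22.8 + 1/17.1) = 0.64 at 107. Multiplying by t of about 2.0, the 95% CI half-width grows from about 1.0 to about 1.3 log10.

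**The case against.** The strongest reply is that 94% is correct for what it describes. It follows directly on the explanation of pooling, so the current design can be read as the pooled 48 vs 36 allocation, in contrast to the base calculation of 36 per group, and not as enrolment achieved. Section 1 openly discloses the early stop and tells the reader to treat inference as exploratory. Planned power enters no analysis, and the confidence intervals required by SAP Section 2.5.2 will show the precision actually achieved.

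Much of this stands. The 94% is not a miscalculation, and nothing is concealed; the sentence is out of date and inconsistent with Section 1. But the pooled allocation at 107 patients does not have 94% power either, and Section 1 supplies no replacement number.

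A second reply is that 73% is the low end. The arm split of the 107 is not documented. A 20% loss may be pessimistic for a Day 29 endpoint in a 112-day treatment epoch. Step-wise Dunnett is more powerful than Bonferroni. The ANCOVA also adjusts for baseline CFU: if the SD of 2.0 is unadjusted and baseline correlates 0.3 to 0.5 with the outcome (an assumption; the documents give no value), the same calculation gives about 78% to 86%. These points are fair, and they are why a range is given. Using step-wise Dunnett or adjusting for baseline would also raise the figure at 180 patients, so 73% remains the like-for-like counterpart of 94%.

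**Conclusion.** The concern holds. The 94% is the power of the 180-patient plan, and the SAP presents it as current after reporting that 107 were randomized. On the SAP's own method the figure is about 73%, a miss probability of about 27% instead of 6%. Depending on loss and test, the variants computed above for 107 patients run from 72% to 86.5%, and none reaches 94%.

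These figures assume that the 107 split at the planned ratios and that the SD is 2.0; the 73% also assumes the planned 20% loss. The disclosure in Section 1 limits the harm, so this is a correction that should be made, not a flaw that undermines the analysis.

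**What to change.** In SAP Section 3, keep the calculation as the original plan, state that 94% applied to 180 randomized patients, and remove the reference to the current study design from that sentence. Then add, with a cross-reference to Section 1, wording such as:

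*Assuming the 107 randomized patients are split at the planned ratios (about 21 pooled placebo and 28–29 per dose) and 20% loss, power per dose for a 2.0 log10 difference is about 73% (Bonferroni) or 77–83% (step-wise Dunnett). With no loss the Bonferroni figure is 84%. With 20% loss, 94% power applies to a difference of about 2.6 log10.*

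The expected CI half-width (about 1.3 log10 against 1.0 as planned) would be a useful companion. If the actual arm counts can be used without compromising the blind, they should replace the assumed split.

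The cost is SAP wording only: no test, estimate, data collection or conduct changes. The stated power becomes less favourable.

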5.1 Imputation rules for complete or partial missing dates

5.1.1 Study drug

When the date of the last dose of study drug is missing for a patient in the SAF, all efforts should be made to obtain the date from the investigator. If it is still missing after all efforts, then the last visit date when study drug was returned will be used in the calculation of treatment duration.

5.1.2 Adverse event start date imputation

The following table explains the notation used in the logic matrix. Please note that **missing start dates** will not be imputed.

	Day	Month	Year
Partial Adverse Event Start Date	Not used	MON	YYYY
Treatment Start Date	Not used	TRTM	TRTY

The following matrix explains the logic behind the imputation.

	MON MISSING	MON < TRTM	MON = TRTM	MON > TRTM
YYYY MISSING	(D) No convention	(D) No convention	(D) No convention	(D) No convention
YYYY < TRTY	(D) Before Treatment Start	(D) Before Treatment Start	(D) Before Treatment Start	(D) Before Treatment Start
YYYY = TRTY	(o) Uncertain	(o) Before Treatment Start	(o) Uncertain	(o) After Treatment Start
YYYY > TRTY	(D) After Treatment Start	(D) After Treatment Start	(D) After Treatment Start	(D) After Treatment Start

Before imputing AE start date, find the AE start reference date.

- If the (imputed) AE end date is complete and the (imputed) AE end date < treatment start date then AE start reference date = min (informed consent date, earliest visit date).
- Else AE start reference date = treatment start date

Impute AE start date -

- If the AE start date year value is missing, the date uncertainty is too high to impute a rational date. Therefore, if the AE year value is missing, the imputed AE start date is set to NULL.

- If the AE start date year value is less than the treatment start date year value, the AE started before treatment. Therefore:
- If AE month is missing, the imputed AE start date is set to the mid-year point (01JulYYYY).
- Else if AE month is not missing, the imputed AE start date is set to the mid-month point (15MONYYYY).
- If the AE start date year value is greater than the treatment start date year value, the AE started after treatment. Therefore:
- If the AE month is missing, the imputed AE start date is set to the year start point (01JanYYYY).
- Else if the AE month is not missing, the imputed AE start date is set to the later of (month start point (01MONYYYY), AE start reference date + 1 day).
- If the AE start date year value is equal to the treatment start date year value:
 - And the AE month is missing the imputed AE start date is set to the AE reference start date + 1 day.
 - Else if the AE month is less than the treatment start month, the imputed AE start date is set to the mid-month point (15MONYYYY).
 - Else if the AE month is equal to the treatment start date month or greater than the treatment start date month, the imputed AE start date is set to the later of (month start point (01MONYYYY), AE start reference date + 1 day).

If complete (imputed) AE end date is available and the imputed AE start date is greater than the (imputed) AE end date, then imputed AE start date should be set to the (imputed) AE end date.

5.1.3 Adverse event end date imputation

- If the AE end date month is missing, the imputed end date should be set to the earliest of the (treatment follow up period date, 31DECYYYY, date of death).
- If the AE end date day is missing, the imputed end date should be set to the earliest of the (treatment follow up period date, last day of the month, date of death).
- If AE year is missing or AE is ongoing, the end date will not be imputed.

5.1.4 Relative day of AE onset and AE end imputations

The relative day of AE onset will be calculated as follows:

- AE start date - date of first dose of study drug (if AE start date is completely known)
- missing (if AE onset date is incomplete or unknown)

The relative day of AE end will be calculated as follows:

- AE end date – date of first dose of study drug (if AE end date is completely known)
- missing (if AE end date is incomplete or unknown)

The duration of an AE will be calculated as follows:

- AE end date – AE start date + 1 (when both dates are completely known)

- Date of end of study completion/discontinuation – AE start date + 1 (when the AE onset date is fully known but the AE is not resolved at the end of the trial): in this case the duration will be presented as “>x days” in the listing rather than “x days”
- missing (when the AE start date is incomplete or unknown, or when the AE has resolved but with an incomplete or unknown end date, or when the AE onset date is > date of end of completion/discontinuation and the AE is not resolved)

5.1.5 Concomitant medication start date imputation

The following table explains the notation used in the logic matrix. Please note that missing start dates will not be imputed.

	Day	Month	Year
Partial CMD Start Date	Not used	MON	YYYY
Treatment Start Date	Not used	TRTM	TRTY

The following matrix explains the logic behind the imputation.

	MON MISSING	MON < TRTM	MON = TRTM	MON > TRTM
YYYY MISSING	(D) Uncertain	(D) Uncertain	(D) Uncertain	(D) Uncertain
YYYY < TRTY	(o) Before Treatment Start	(o) Before Treatment Start	(o) Before Treatment Start	(o) Before Treatment Start
YYYY = TRTY	(o) Uncertain	(o) Before Treatment Start	(o) Uncertain	(o) After Treatment Start
YYYY > TRTY	(o) After Treatment Start	(o) After Treatment Start	(o) After Treatment Start	(o) After Treatment Start

- If the CM start date year value is missing, the imputed CM start date is set to 1 day prior to treatment start date.
- If the CM start date year value is less than the treatment start date year value, the CM started before treatment. Therefore:
 - If the CM month is missing, the imputed CM start date is set to the mid-year point (01JulYYYY).
 - Else if the CM month is not missing, the imputed CM start date is set to the mid-month point (15MONYYYY).
- If the CM start date year value is greater than the treatment start date year value, the CM started after treatment. Therefore:
 - If the CM month is missing, the imputed CM start date is set to the year start point (01JanYYYY).

- Else if the CM month is not missing, the imputed CM start date is set to the month start point (01MONYYYY).
- If the CM start date year value is equal to the treatment start date year value:
 - And the CM month is missing or the CM month is equal to the treatment start date month, then the imputed CM start date is set to 1 day prior treatment start date.
 - Else if the CM month is less than the treatment start date month, the imputed CM start date is set to the mid-month point (15MONYYYY).
 - Else if the CM month is greater than the treatment start date month, the imputed CM start date is set to the month start point (01MONYYYY).

If complete (imputed) CM end date is available and the imputed CM start date is greater than the (imputed) CM end date, then imputed CM start date should be set to the (imputed) CM end date.

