13. Patients who have had a pulmonary exacerbation requiring systemic glucocorticosteroid treatment and/or antibiotics in the 4 weeks prior to Visit 1. In the event of an exacerbation occurring during the screening epoch, the patient must discontinue from the study. The patient may be rescreened once the inclusion/exclusion criteria have been met.
14. Patients with active pulmonary tuberculosis.
15. Patients currently receiving treatment for nontuberculous mycobacterial (NTM) pulmonary disease.
16. Patients with one or more positive cultures in the last 12 months for *Mycobacterium avium* complex, *M. abscessus* complex, *M. kansasii*, *M. malmoense*, *M. xenopi*, *M. simiae* or *M. cheloneae*, unless all subsequent NTM cultures (at least two) are negative and in the opinion of the investigator the patient does not meet ATS criteria for NTM-pulmonary disease.
17. Hemoptysis of more than 60 mL at any time within 30 days prior to study drug administration (Visit 101).
- 18a. Estimated glomerular filtration rate (eGFR) of 50 mL/min/1.73m² or less, or an abnormal urinalysis defined as 2+ or greater proteinuria at screening (Visit 1).
19. Patients with clinically significant laboratory abnormalities (not associated with the study indication) at screening (Visit 1).
20. Patients with primary immunodeficiency receiving immunoglobulin therapy.
- 21a. Patients with primary ciliary dyskinesia (PCD) may be eligible if their hearing threshold at screening audiometry is 25dB or lower at frequencies 0.5-4 kHz.
22. Patients with active allergic bronchopulmonary aspergillosis.
23. Patients with an organ and bone marrow transplant/grant versus host disease.
24. Patients with haematological malignancies.
25. Patients with other clinically significant conditions (not associated with the study indication) at screening which might interfere with the assessment of this study.
26. Patients who are receiving inhaled anti-pseudomonal antibiotic within 28 days prior to study drug administration (Visit 101).
27. Any use of systemic anti-pseudomonal antibiotics within 28 days prior to study drug administration (Visit 101).
28. Use of loop diuretics, i.v. urea, i.v. mannitol within 7 days prior to study drug administration (Visit 101).

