2.6.3.3 Anti-pseudomonal antibiotics

Proportion of patients requiring anti-pseudomonal antibiotics

The proportion of patients requiring anti-pseudomonal antibiotics across the treatment epoch and across the entire study period will be summarized by treatment arm and by route of administration (overall, oral and parenteral).

Time to first use of anti-pseudomonal antibiotics across the entire study period

The time to first use of anti-pseudomonal antibiotics by route of administration (overall, oral and parenteral) will be analyzed using a Cox regression model stratified by baseline macrolide use. The model will include treatment as a fixed-effect factor, and number of pulmonary exacerbations in the 12 months prior to screening as a covariate. Six pairwise comparisons will be evaluated as specified in [Section 2.6.3](#). in addition two pairwise comparisons will be evaluated between pooled continuous regimens vs pooled placebo and, between pooled cyclic regimens and pooled placebo. The estimated adjusted hazard ratio for TIP over placebo will be displayed along with the associated 2-sided 95% CI.

The exposure adjusted rate of usage of anti-pseudomonal antibiotics across the entire study period

The number of anti-pseudomonal antibiotics across the entire study period will be analyzed by route of administration (overall, parenteral and oral) using a generalized linear model assuming the negative binomial distribution including treatment and baseline macrolide use as fixed-effect factors, and number of pulmonary exacerbations in the 12 months prior to screening as a covariate. The log time in study in years will be included as an offset variable in the model. Six pairwise comparisons will be evaluated as specified in [Section 2.6.3](#), in addition two pairwise comparisons will be evaluated between pooled continuous regimens vs pooled placebo and, between pooled cyclic regimens and pooled placebo. The adjusted rate of usage will be provided for each treatment arm. The estimated rate ratio together with the 2-sided 95% interval will be provided.

Duration of anti-pseudomonal antibiotic use across the entire study period

The duration of anti-pseudomonal antibiotic use (days) across the entire study period will be summarized by cohort, treatment arm and pooled cyclic and continuous regimens and by route of administration (overall, parenteral and oral).

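### SAP 5.1.5 dates an anti-pseudomonal antibiotic with a missing start day in the treatment-start month to the day before first dose, a date exclusion 27 rules out for an eligible patient, so on-study first uses can be misdated or lost

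*SAP*

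**What the plan says.** SAP 5.1.5 covers partial start dates of concomitant medications. Where the start year equals the treatment-start year, the rule is triggered by this condition: "And the CM month is missing or the CM month is equal to the treatment start date month". The result is: "then the imputed CM start date is set to 1 day prior treatment start date". The matrix in the same section labels these two cells as uncertain, not as before treatment start. The only use of the end date is a cap that applies under this condition: "If complete (imputed) CM end date is available and the imputed CM start date is greater than the (imputed) CM end date". The start is then moved back to the end date, so the cap can only make a start earlier.

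These dates feed an efficacy analysis. SAP 2.6.3.3 states: "The time to first use of anti-pseudomonal antibiotics by route of administration (overall, oral and parenteral) will be analyzed using a Cox regression model". The same section models the number of anti-pseudomonal antibiotics over the study with a negative binomial model.

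Exclusion 27 in Protocol 4.2 reads "Any use of systemic anti-pseudomonal antibiotics within 28 days prior to study drug administration (Visit 101", which is Day 1.

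The adverse event rule in SAP 5.1.2 points the other way. For a missing month in the treatment year: "And the AE month is missing the imputed AE start date is set to the AE reference start date + 1 day". For a known month equal to the treatment-start month, it takes the later of the first of the month and the reference date plus one day. The reference date is the treatment start unless the event ended before treatment.

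**The concern.** Dating an uncertain start to just before treatment is a usable default for background medication. It does not suit a drug class whose first on-study use is an endpoint and whose use in the preceding four weeks is an exclusion. For that class the protocol already says on which side of first dose a same-month start should fall, and the rule chooses the other side.

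Time to first use is at stake, and possibly the usage rate. An exacerbation and the antibiotic given for it, both recorded with the same month and no day, would also be dated on opposite sides of first dose.

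**Working it through.** There is no plan figure to reproduce, because this is a date rule. The check applies it literally.

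**Inputs.** Imputed start = first dose − 1 day (SAP 5.1.5). Look-back = 28 days before first dose (Protocol 4.2, exclusion 27). Let d be the day of the month of first dose and s the true start day in the same month.

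**Step 1: the imputed date.** It is always 1 day before first dose, and 1 ≤ 28, so it always lies inside the look-back. If d = 1, it also falls outside the month that was recorded.

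**Step 2: where the true start can lie.** A pre-dose start is permitted only if d − s > 28. The earliest day is s = 1, so this needs d ≥ 30. Day 30 occurs in 11 months and day 31 in 7, giving 18 dates. 365 − 18 = 347, and 347/365 = 95%. On those 347 dates an eligible patient's same-month start must be on or after first dose.

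**Step 3: share of permitted start days on or after first dose.** Assumption: d and s are uniform over the month, since the documents give no distribution.

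| Month length | All pairs | s ≥ d | Permitted pre-dose pairs | s ≥ d, of all | s ≥ d, of permitted |
|---|---|---|---|---|---|
| 28 | 784 | 406 | 0 | 51.8% | 100% |
| 30 | 900 | 465 | 1 | 51.7% | 99.8% |
| 31 | 961 | 496 | 3 | 51.6% | 99.4% |

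Without the exclusion the rule would be wrong about half the time. With it, the rule is wrong in nearly every case.

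**Step 4: missing month.** The same count over a 365-day year gives 66,795 pairs with s ≥ d and 56,616 permitted pre-dose pairs. 66,795/(66,795 + 56,616) = 54%. The 95% therefore does not carry over to missing-month records.

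**Step 5: example.** First dose is 5 March. The antibiotic is recorded as March with the day unknown, and its true start is 20 March (study day 16).
- SAP 5.1.5 gives 4 March.
- The adverse event rule gives 6 March for the same partial date.
- If starts count only from first dose, the use is lost, and the patient is censored or credited with a later course.
- SAP 2.1.1 defines study day before first dose as first dose minus the date of interest. Read literally, 4 March is then study day 1, and the use moves 15 days early (16 − 1).

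The SAP does not say which handling applies. The timing is wrong under both.

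**Step 6: arm size.** SAP 1 gives 107 randomized. At 1:1:1 and then 2:2:1, each active arm has about 107/3 × 2/5 = 14 patients, so single records can matter in the six comparisons of SAP 2.6.3.

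**The case against.** The strongest reply is that the consequences depend on steps the SAP does not describe.

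- **Loss of uses.** A reader might infer that on-study first uses are removed and the proportion treated is understated. The documents do not establish this. SAP 2.4.2 keeps a medication concomitant if it starts before first dose and continues after it. SAP 5.1.6 sets a missing end day to the earlier of month end and treatment end, so such courses usually still overlap treatment. SAP 2.6.3.3 does not restrict first use to starts from Day 1. This stands: a wrong date is certain under the rule, but loss is only possible.
- **Eligibility.** A reader might infer that the rule creates false breaches of exclusion 27 and shrinks the per-protocol set. SAP 2.2 leaves deviation criteria to the data validation specifications and to review at a blinded meeting. It does not say that imputed dates are used. The imputed date would look like a breach only if it were used there.
- **Frequency.** Protocol 6.4.4 calls for an unscheduled visit within 2 working days of an exacerbation, Protocol 8.3 provides for data queries, and SAP 2.6.1.2 has concomitant medications reviewed on an ongoing basis. These make partial on-study dates less likely. They do not correct the rule where one occurs.
- **Weight.** The endpoints are secondary and unadjusted for multiplicity, the primary sputum analysis does not use these dates, and SAP 1 calls the inference exploratory. This limits the importance of the point but does not make the date right.

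**Conclusion.** The rule is wrong for systemic anti-pseudomonal antibiotics with a known month equal to the treatment-start month and a missing day. For an eligible patient the imputed date is never possible, and on 95% of first-dose dates the true start must be on or after first dose. First use can be misdated, or lost under one reading of the analysis.

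The 95% is a share of calendar dates, not of records or patients, and covers same-month records only. It assumes that exclusion 27 was respected. The number of affected records cannot be derived from the documents, so the effect on any hazard or rate ratio is not quantified. The rule is the same in every arm, and the documents give no basis for saying which comparison it would favour. The point merits a short correction and does not threaten the primary analysis.

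**What to change.** Add to SAP 5.1.5: for anti-pseudomonal antibiotics with a known start month equal to the treatment-start month and a missing day, impute the treatment start date, unless the end date is before first dose. This follows the direction and the end-date logic of the adverse event rule, one day apart from it. Keep the current rule for other medications and for a missing month or year. Add to SAP 2.2 that eligibility deviations are judged on recorded dates, not imputed ones.

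The cost is two sentences. These uses would be dated as early as possible, on Day 1, so time to first use is biased early for them: in the example, 5 March for a true start of 20 March. A rare true pre-dose use could also count as on-study. The gain is that the use is counted whichever handling of pre-dose starts is programmed.
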